1.0 Background & Rationale

Gastrointestinal (GI) cancers are among the most common cancers in the United States, and the majority are discovered at advanced stages.¹ Fatigue is a highly prevalent symptom in advanced GI cancer patients, with up to 68% reporting moderate to severe fatigue.^{2, 3} Furthermore, when asked to rank symptoms and concerns, fatigue was the top concern for 62% of advanced colorectal cancer patients.⁴ Fatigue often co-occurs with a number of other symptoms and substantially impacts daily activities and quality of life (QoL).^{3, 5-8} Among advanced cancer patients, fatigue and related symptoms have been linked to prolonged hospitalizations and readmissions.⁹ In our pilot work with advanced GI cancer patients ($N=51$), 67% reported moderate to severe difficulty initiating activities due to fatigue.

Treatments for fatigue have limited empirical support in advanced cancer,¹⁰⁻¹² leading to a critical unmet need for fatigue management in advanced GI cancer patients.^{3, 4} A Cochrane meta-analysis evaluated randomized controlled trials (RCTs) of 18 pharmacologic treatments for fatigue in patients with advanced cancer and other late-stage chronic diseases.¹⁰ Given the limitations of the evidence (e.g., small, heterogeneous samples) and minimal effect sizes in many trials, the authors did not make recommendations for fatigue treatment in these populations. Another Cochrane meta-analysis of 14 behavioral interventions for fatigue in advanced cancer, most of which were cognitive-behavioral and supportive-expressive therapies, drew similar conclusions.¹² Of note, only two intervention trials had a fatigue eligibility criterion.

As fatigue and related symptoms interfere with patients' daily functioning, family caregivers often assume a range of new responsibilities.¹³⁻¹⁶ Our team found that among family caregivers of advanced GI cancer patients ($N=50$), 48% reported that they did not have enough time for themselves due to caregiving, and 76% reported moderate to severe stress due to balancing caregiving with other work and family obligations. Both of these reports and global caregiving burden were associated with reduced mental QoL, including symptoms of anxiety and depression ($\beta = -.30$ to $-.66$). Similarly, in population-based research, cancer caregivers reported greater activity impairment and worse QoL than non-caregivers.¹⁷

Evidence-based interventions to reduce family caregiver burden in advanced cancer are lacking. Most behavioral interventions for cancer caregivers have been delivered to patient-caregiver dyads coping with early-stage breast or prostate cancer and did not have a symptom or distress criterion for study entry.¹⁸⁻²⁰ These interventions yielded small to medium effects on caregiver burden and QoL.¹⁸⁻²⁰ In addition, the limited RCTs with advanced cancer patient-caregiver dyads generally did not target those at greater risk for poor outcomes (e.g., those with high symptom interference with functioning or caregiving burden).²¹⁻²³ Thus, the generalizability of research findings to subgroups most in need of intervention has yet to be determined.

The significance of this trial is strengthened by the use of Acceptance and Commitment Therapy (ACT), a theory-driven behavioral approach,²⁴ to address fatigue interference with functioning in advanced GI cancer patients and caregiver burden. The goal of ACT is to increase psychological flexibility so that unwanted internal experiences (e.g., physical symptoms, feelings, thoughts) interfere less with meaningful activities.^{24, 25} Psychological flexibility is defined as fully experiencing the present moment while

persisting in actions aligned with personal values.²⁴ ACT has a strong evidence base in chronic pain^{26, 27} and mental health.^{28, 29} A meta-analysis of 39 RCTs found that ACT was superior to control conditions for somatic symptoms (effect size [ES]=.58), anxiety/depression (ES=.37), and other mental disorders (ES=.92), representing a moderate to large treatment effect.²⁹ ACT has not been tested in caregivers of adults, with the exception of one RCT for dementia caregivers with high depressive symptoms.³⁰ In this trial, ACT led to similar or better mental health outcomes than cognitive-behavioral therapy (CBT).

ACT has also produced promising findings in pilot trials with cancer patients.^{25, 31-33}

In one trial, late-stage ovarian cancer patients were randomly assigned to 12 in-person sessions of ACT or 12 in-person sessions of CBT.³³ ACT participants showed large and significantly greater improvement in general distress ($d = .89$), global QoL ($d = 1.35$), anxiety ($d = 1.26$), and depressive symptoms ($d = 1.69$) than CBT participants over the intervention period. Notably, all attrition was due to death or beginning hospice; thus, ACT appeared to be feasible and acceptable to patients. Other pilot feasibility trials of ACT in cancer have also found positive changes in psychological outcomes.^{25, 31} For example, Feros and colleagues tested a 9-session ACT intervention for distressed patients with various cancers.²⁵ General distress, mood, and global QoL significantly improved immediately post-intervention and three months later compared to baseline. Effect sizes for general distress and mood were large, and the effect size for global QoL was medium. These pilot data suggest that ACT warrants further study in cancer. Indeed, our team extended prior pilot studies by using telephone-based ACT to target fatigue interference and related outcomes in 47 MBC patients.³⁴ The intervention showed strong evidence of feasibility and promise with respect to fatigue and sleep interference relative to an education/support condition. Regarding feasibility, the majority (64%) of patients who could be reached via phone were screened for eligibility, and 100% of eligible patients consented. Additionally, retention was good with 83% of the entire sample completing the 8-week follow-up, and 79% completing the 12-week follow-up. Fatigue interference showed moderate reduction across time in the ACT group and minimal change in the education/support group; the between-group effect size was -.30 at 12 weeks. Furthermore, when examining the subsample ($n = 24$) with moderate to severe fatigue interference at baseline, the between-group effect size was -.59 at 12 weeks. ACT participants also showed decreased sleep interference at 12 weeks, with a between-group effect size of -.40 in the full sample and -.61 in the subsample with moderate to severe fatigue interference. Differences between study conditions were not significant; however, because it was a pilot study, we focused our analyses on effect sizes rather than statistical significance.

ACT can be widely disseminated to clinicians who care for advanced GI cancer patients and caregivers. Training in ACT is widely available and accessible to clinicians with various professional backgrounds, levels of education, and theoretical orientations.

Furthermore, rather than being a fixed set of specific techniques, ACT draws from a broad range of traditional behavior therapy approaches as well as those outside the behavioral tradition (e.g., acceptance, mindfulness, identification of personal values).^{24, 35} Thus, ACT is an adaptable approach that can be delivered as a stand-alone therapy and/or integrated into existing therapeutic approaches.

2.0 Study Objectives

Building on patient-focused ACT pilots in cancer,^{25, 33, 34} this NCI-funded pilot trial tests a novel, dyadic telephone-based ACT program for addressing both fatigue interference (i.e., fatigue's negative impact on activities, mood, and cognition) in advanced GI cancer patients and family caregiver burden. In order to enhance translation to geographically dispersed individuals and those with high symptom burden or functional impairments, we will deliver the intervention via phone. Advanced GI cancer patients with moderate to severe fatigue interference and their primary family caregivers with significant caregiving burden ($N=50$ dyads) will be randomized to six weekly 50-minute telephone sessions of either (1) ACT or (2) education/support. ACT includes acceptance and mindfulness meditation exercises, identification of personal values, and engagement in activities consistent with these values. Examples of dyadic intervention components include joint mindfulness practices and having each participant describe the other person's strengths and resources for goal achievement. Feasibility will be examined via accrual, attrition, and adherence rates, and acceptability will be evaluated using a mixed methods approach (qualitative and quantitative). Outcomes will be assessed at baseline, 2 weeks post-intervention, and 3 months post-intervention. Findings will inform an R01 application to conduct a large-scale RCT of intervention efficacy. The study objectives are:

2.1 Primary Objective: To evaluate the feasibility and acceptability of delivering telephone-based ACT to advanced GI cancer patients and their caregivers.

2.2 Secondary Objective: To test the effects of telephone-based ACT on patient fatigue interference and caregiver burden (primary outcomes) as well as patient sleep interference and patient and caregiver engagement in daily activities, progress in value-based living, psychological flexibility, and QoL (secondary outcomes).

Hypothesis: ACT will lead to improved primary and secondary outcomes as compared to education/support.

2.3 Exploratory Objective:

To explore the effects of telephone-based ACT on patient and caregiver physical and mental health service use (tertiary outcomes).

3.0 Outcome Measures/Endpoints

All outcomes will be assessed at baseline, 2 weeks post-intervention, and 3 months post-intervention (see Table 1 of section 5.0 for complete timing details and assessment windows).

3.1 Primary Outcome Measures:

The primary outcome measure for patients is the 7-item Fatigue Interference subscale of the Fatigue Symptom Inventory (FSI).^{36, 37} The primary outcome measure for caregivers is the 12-item short form of the Zarit Burden Interview,^{38, 39} which evaluates caregiving burden (i.e., personal strain and role strain due to caregiving).

3.2 Secondary Outcome Measures:

- (1) Patient sleep interference will be assessed with the 8-item Patient-Reported Outcomes Measurement Information System (PROMIS) sleep-related impairment measure.^{40, 41} This measure assesses the perceived interference of sleep problems with activities, mood, and cognition.

- (2) Patient and caregiver engagement in daily activities will be assessed with the 6-item PROMIS short-form measure of ability to participate in social roles and activities.⁴² The items, which are reverse-coded, measure difficulty engaging in social and recreational activities as well as usual work (including housework).
- (3) Patient and caregiver progress in value-based living will be assessed with the 5-item Value Progress subscale of the Valuing Questionnaire.⁴³
- (4) Patient and caregiver psychological flexibility will be evaluated with the 7-item Acceptance and Action Questionnaire-II (AAQ-II).⁴⁴
- (5) QoL. Patient QoL will be assessed with the 15-item McGill Quality of Life Questionnaire—Revised, which was designed for patients with life-threatening illnesses.⁴⁵ Caregiver QoL will be assessed with the 10-item PROMIS measure of global health.⁴⁶

4.0 Eligibility Criteria

4.1 Patient Inclusion Criteria:

- Patient is at least 3 weeks post-diagnosis of unresectable stage III or stage IV gastrointestinal cancer (i.e., anal, colon, esophageal, gallbladder, liver, pancreatic, rectal, small intestine, or stomach cancer) and is receiving care at the Indiana University Simon Cancer Center or Eskenazi Health.
- Patient is at least 18 years of age.
- Patient has adequate English fluency for study participation.
- Patient is willing to participate in this study.
- Patient has moderate to severe fatigue interference (i.e., mean score ≥ 2.5 on the Fatigue Interference subscale of the Fatigue Symptom Inventory)^{36, 37}
- Patient has an eligible, consenting family caregiver (see criteria below)

4.2 Patient Exclusion Criteria:

- Patient makes 3 or more errors on a validated 6-item cognitive screener⁴⁷ or exhibits significant psychiatric or cognitive impairment (dementia/delirium, intellectual disability, active psychosis) that in the judgment of the investigators would preclude providing informed consent and study participation.
- Patient Generated Subjective Global Assessment (PG-SGA; the patient-reported version of the Eastern Cooperative Oncology Group score) >2 .⁴⁸
- Patient is receiving hospice care at screening.
- Patient does not have working phone service.
- Patient has hearing impairment that precludes participation.

Note: Patients who enroll in hospice during the trial will have the option of continuing trial participation.

4.3 Caregiver Inclusion Criteria:

- Family caregiver identified by an unresectable stage III or stage IV gastrointestinal cancer patient who meets the eligibility criteria.

- Caregiver lives with the patient or has visited the patient in-person at least twice a week for the past month.
- Caregiver is at least 18 years of age.
- Caregiver has adequate English fluency for study participation.
- Caregiver is willing to participate in this study.
- Caregiver has moderate to severe caregiving burden, defined as a score ≥ 6 on the 6-item Zarit Burden Interview³⁹ or a T-score ≥ 60 (at least one standard deviation above the population mean) on the 4-item PROMIS anxiety or depression measures.⁴⁹

4.4 Caregiver Exclusion Criteria:

- Caregiver exhibits significant psychiatric or cognitive impairment (dementia/delirium, retardation, active psychosis) that in the judgment of the investigators would preclude providing informed consent and study participation.
- Caregiver does not have working phone service.
- Caregiver has hearing impairment that precludes participation.
- Patient declines study participation.

5.0 Study Design

The study procedures are shown in **Table 1**. Advanced GI cancer patients and caregivers ($N = 50$ dyads) who meet eligibility criteria and provide informed consent will be randomized to receive either six weekly sessions of the ACT intervention or the education/support condition. Outcomes will be assessed via telephone at baseline and approximately 2 weeks and 3 months post-intervention within the timing windows outlined below.

Table 1

Timing	Procedure and person(s) responsible
At least 3 weeks after the patient's advanced GI cancer diagnosis	
(1) The research assistant will contact potentially eligible patients, screen patients for eligibility, and obtain informed consent, which can be done verbally over the phone or face to face in the outpatient clinics at the IU Simon Cancer Center or Eskenazi Health (see "recruitment process" below).
 
(2) The research assistant will contact potentially eligible caregivers, screen caregivers for eligibility, and obtain informed consent, which can be done verbally over the phone or face to face in the outpatient clinics at the IU Simon Cancer Center or Eskenazi Health (see "recruitment procedures" below). If the caregiver is not eligible or does not consent to participate, then the patient will be informed that s/he is not eligible for the study.

Target date = about 1 week after recruitment of the patient and caregiver. The baseline assessment can be completed up to 1 month after recruitment.	(3) Patients and caregivers who consent to participate will complete a 30- or 25-minute baseline assessment over the phone, respectively (see "interview procedures" below). The interview will be administered by a trained research assistant or a trained doctoral student in clinical psychology.
Sessions will occur approximately 1 week from each other, with the first session occurring about 1 week following the baseline assessment. Participants will have up to 12 weeks to complete the 6 sessions.	(4) Patients and caregivers will participate in six, 50-minute telephone-based sessions of ACT or education/support. Sessions will be administered by licensed mental health professionals who are supervised by the PI and [name] who are clinical psychologists.
Target date = approximately 2 weeks after the last intervention session. Assessments can be completed as early as 7 days prior to this target follow-up date or as late as 14 days following the target follow-up date.	(5) Patients and caregivers will complete a 30-minute assessment over the phone (see "interview procedures" below). Assessments will be administered by a trained research assistant or a trained doctoral student in clinical psychology who are blinded to the intervention arm.
Target date = within 2 weeks of the 2-week post-intervention assessment. The qualitative interview can be completed as early as the same day as the 2-week follow-up or as late as 21 days after the 2-week follow-up.	(6) Patients and caregivers in the ACT condition will complete a 30-minute qualitative phone interview on intervention acceptability. The interview will be administered by a trained doctoral student in clinical psychology.
Target date = approximately 3 months after the last intervention session. Assessments can be completed as early as 7 days prior to this target follow-up date or as late as 21 days following the target follow-up date.	(7) Patients and caregivers will complete a 25- or 20-minute assessment over the phone, respectively. Assessments will be administered by a trained research assistant or a trained doctoral student in clinical psychology who are blinded to the intervention arm.

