Advanced patients and caregivers ($N = 50$ dyads) who are eligible and provide informed consent will complete individual phone assessments at baseline and approximately 2 weeks and 3 months following the final intervention session (see Table 1 in section 5.0 above for allowable assessment windows). The baseline assessment takes about 30 minutes for patients and 25 minutes for caregivers. Each follow-up assessment takes about 25 minutes for patients and 20 minutes for caregivers. Interviewers will be blind to study condition. Assessments will include questions regarding demographics, medical history, and primary and secondary outcomes. Participants will be provided with copies of response options via email or postal mail to facilitate survey completion (see Appendix E). Patients and caregivers in the ACT condition will also be invited to complete a 30-minute individual qualitative interview about intervention acceptability within approximately two weeks of the 2-week follow-up assessment. Each participant will receive \$40 in Target gift cards via postal mail for each completed assessment (baseline and 2-week and 3-month follow-ups) for a possible total of \$120 in gift cards (\$160 in gift cards for ACT participants only) for their time. There is no cost to study participants. If we cannot reach

a participant for an interview or phone session after several attempts, we will mail them a letter asking them to contact the study team (Appendix C). Table 2 below outlines the assessment schedule at baseline and the two follow-ups.

Table 2. Quantitative Measures						
Domain	Measure	# Items	Baseline	2-week follow-up	3-month follow-up	Administered to Patients (P) or Caregivers (C)
Sociodemographics	Sociodemographics	7-8	X			P, C
Medical comorbidity	Checklist of 8-9 conditions	8-9	X			P, C
Functional status	Patient-reported ECOG	1	X	X	X	P
Cancer information (e.g., date of diagnosis, cancer treatments)	Chart review	n/a	X	X	X	N/A
Intervention acceptability	Intervention acceptability scale	6		X		P, C
Primary patient outcome: fatigue interference	Fatigue interference subscale of FSI	7	X	X	X	P
Primary caregiver outcome: caregiving burden	12-item short-form of Zarit Burden Interview	12	X	X	X	C
Secondary outcomes:						
• Sleep interference	PROMIS short-form sleep-related impairment measure	8	X	X	X	P
• Engagement in daily activities	PROMIS short-form measure of ability to participate in social roles and activities	6	X	X	X	P, C

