11.0 Statistical Considerations

Aim 1. Feasibility and acceptability will be evaluated via descriptive statistics for accrual, attrition, and adherence as well as Likert-scale items assessing intervention helpfulness. We will judge this trial as feasible if: 1) $\geq 60\%$ of screened eligible dyads enroll in the study;²¹ and 2) $\geq 70\%$ of enrolled dyads complete 5-6 intervention sessions and all assessments. We will judge this trial as acceptable if $\geq 70\%$ of dyads rate ACT as moderately to extremely helpful (i.e., an average score ≥ 4 on 1 to 5 Likert scale items).

To analyze qualitative data on ACT's acceptability, we will use an immersion/crystallization approach.⁸⁰ Research questions guiding the analysis pertain to the perceived helpfulness of ACT components and their impact on functioning and well-being. Interviews will first be transcribed by a trained research assistant. Analysis of the interview data will consist of two phases: open and focused coding.^{80, 81} In the open coding phase, the analysts (Drs. [name], [name], and a Ph.D. student in clinical psychology) will independently label each line of data to reflect meanings or themes emerging from the text. This is done iteratively, combining, adding, or eliminating themes, until analysts agree on a set of emergent thematic categories (codes). In focused coding, codes derived in open coding are independently applied to all transcripts. Special attention will be paid to negative cases (i.e., data that may call initial observations or interpretations into question).⁸² Transcripts will be divided evenly among analysts, with every fourth transcript coded in common to maintain consistency in coding over time. Analysts will meet bi-weekly to compare commonly-coded transcripts. Discrepancies will be resolved by consensus. Atlas-ti software will facilitate coding, and qualitative results will inform intervention refinement.

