Aim 2. Given that this is a pilot study, our data analytic approach for Aim #2 will be to derive effect size estimates rather than test for statistical significance. A linear mixed-model repeated measures approach (SAS Proc-Mixed) will be used to examine ACT's effects on primary and secondary outcomes. For outcome measures that only patients or caregivers complete (e.g., patient fatigue interference or caregiver burden), models will include main effects of time (as categorical) and study group and the time-by-study group interaction. Treatment effects will be evidenced by the interaction between time and study group (i.e., group mean differences after the intervention but no such differences at baseline). Models will include random intercepts to account for nonindependence of individuals' scores across time. For outcomes reported by patients and caregivers (e.g., psychological flexibility), multilevel modeling for dyadic data will be used.^{83, 84} Models will include the main effects of time, study group, and social role (patient vs. caregiver) as well as all two and three-way interactions between these variables. The time x study group x role interaction will estimate the degree to which treatment effects are different for patients and caregivers. Dyadic models will include random intercepts for patients and caregivers, as well as the covariance between the intercepts to account for nonindependence across time and across partners.

Aim 3. To conduct data analyses for Aim #3, we will use logistic and Poisson regression models to explore the effects of ACT on patient and caregiver physical and mental health service use (e.g., number of patient ER visits, patient and caregiver use of counseling and/or psychiatric medication). Logistic and Poisson regression analyses are appropriate for binary and count outcome data, respectively. Analyses will examine study condition as a predictor of health service use over the entire study period, controlling for baseline service use. Support service referrals will be a covariate in analyses of mental health service use.

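### The follow-up anchor is undefined for dyads that do not complete session 6: their first visit is due up to about 5 weeks before that of weekly-pace completers, or has no date at all

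*Combined protocol and SAP*

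**What the plan says.** Table 1 (section 5.0) times both follow-ups from the same event: "Target date = approximately 2 weeks after the last intervention session" and "Target date = approximately 3 months after the last intervention session". The first has the window "Assessments can be completed as early as 7 days prior to this target follow-up date or as late as 14 days following the target follow-up"; the second may be 7 days early "or as late as 21 days following the target follow-up date". Interview Procedures in section 7.0 puts the assessments "approximately 2 weeks and 3 months following the final intervention session".

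Sessions are about weekly, and the first is about 1 week after baseline. The pace may be slower: "Participants will have up to 12 weeks to complete the 6 sessions". Section 6.0 places randomisation after the baseline assessment and so before any session.

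Aim 1 in section 11.0 requires that at least 70% "of enrolled dyads complete 5-6 intervention sessions and all assessments". For Aim 2 the "models will include main effects of time (as categorical) and study group and the time-by-study group interaction", and the interaction is read as the treatment effect.

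Section 10.0 withdraws both members of a dyad if either dies, becomes medically unable to continue or decides to stop participation. It does not say that stopping sessions, by itself, ends follow-up.

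**The concern.** The clock for both outcome visits starts at an event that happens after randomisation and depends on how far a dyad gets through the programme. The plan does not define that event for a dyad that never reaches session 6. Staff must then either schedule from whatever session turned out to be the last, or leave the dyad without a date.

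The Aim 2 model uses the visit label, not elapsed time. Values taken well before the programme would have ended are pooled with values taken after it. If early stopping or session pace differed between ACT and education/support, the two arms would be compared at different times since randomisation under one label. A dyad with no date may simply not be measured, so whether an outcome exists would depend on adherence. The effect sizes from Aim 2 are meant to inform a larger efficacy trial.

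**Working it through.** The plan gives no follow-up date in weeks from baseline, so there is no figure of its own to reproduce. The check is calendar arithmetic.

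**Inputs.** Baseline = week 0. Session 1 = week 1, then weekly, so session *k* falls in week *k* (Table 1). First window −1/+2 weeks and second window −1/+3 weeks (Table 1, days converted). Assumption: 3 months = 13 weeks.

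**Formulas.** First target = week of anchor session + 2. Second target = week of anchor session + 13.

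**Reading A: the anchor is the last session attended, weekly pace.**

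| Sessions attended | First target (window) | Second target (window) | Gap to weekly completer |
|---|---|---|---|
| 1 | 1+2 = 3 (2–5) | 1+13 = 14 (13–17) | 5 weeks |
| 2 | 4 (3–6) | 15 (14–18) | 4 weeks |
| 3 | 5 (4–7) | 16 (15–19) | 3 weeks |
| 4 | 6 (5–8) | 17 (16–20) | 2 weeks |
| 5 | 7 (6–9) | 18 (17–21) | 1 week |
| 6 | 6+2 = 8 (7–10) | 6+13 = 19 (18–22) | 0 |

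After one or two sessions the first window closes (week 5 or 6) before the completers' window opens (week 7). After five sessions the shift is smaller than the 3-week window itself.

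Reading A also has an operating problem. The first window closes 2 + 2 = 4 weeks after the anchor session. A dyad that pauses after session 1 would have its window closed at week 5, yet it may resume until week 12 or 13. At week 5 nobody can know that session 1 was the last.

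**Reading B: the anchor is session 6.** A dyad that does not hold session 6 has no target date for either visit.

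**No session.** No date can be computed under A or B.

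**Which reading fits the plan?** Aim 1 counts a dyad with five sessions and all assessments as complete. Under B, a dyad that stops after session 5 could never have a dated assessment; it could qualify only if the missed session was an earlier one and session 6 took place. Reading A fits more naturally, but the text does not state it.

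**Spread among completers.** The plan does not say where the 12 weeks start. From baseline, session 6 is at latest week 12: first target 12+2 = 14, second 12+13 = 25. From session 1, it is at latest week 13: first target 15, second 26. Against week 8, the first target is 14−8 = 6 or 15−8 = 7 weeks later.

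**The case against.** Timing an outcome from the end of the programme is a coherent choice for a post-intervention measure, and nothing in the documents says attended. A reader might infer that the plan schedules early stoppers weeks ahead of completers. It does not say so; that follows only under Reading A at a similar pace, and a slow early stopper could be measured at the same time as a weekly-pace completer, or later. This part of the objection stands. It does not remove the gap, because Reading B leaves the same dyads undated.

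Section 10.0 will take some early stoppers out of the study altogether, so the group at issue is smaller than all non-completers. That stands too. But the section ties removal to stopping participation or not following study rules, so dyads that only stop sessions can remain.

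A reader might also quote a range of week 2 to week 17 for the first visit. That sets the early window edge after one session against the late edge for a 12-week completer. Most of the spread in targets comes from the 12-week allowance, not from stopping early.

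Finally, a reader might infer that the treatment comparison is biased. The documents do not support that. They give no session-completion rates for this trial. The number, order and length of sessions are the same in both arms, and so is the allowance. The only trajectories reported, from the pilot in metastatic breast cancer (section 1.0), show minimal change under education/support. The trial is a pilot whose primary objective is feasibility and acceptability, and Aim 2 estimates effect sizes rather than testing significance. Unequal timing between arms is a possibility that the rule leaves open, not a shown effect.

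**Conclusion.** The point holds in a limited form. The anchor for both follow-ups is undefined for dyads that do not complete session 6. If it is the last session attended, dyads that stop sessions but stay in the study have targets 1 to 5 weeks before weekly-pace completers: 5 weeks after one session, 1 week after five. If it is session 6, they have no target. Randomised dyads with no session have none on either reading. Separately, the allowance spreads completers' first target by about 6 to 7 weeks.

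These figures assume session 1 at week 1, weekly pace for early stoppers, and 3 months taken as 13 weeks. The number of dyads affected, any difference between arms and the effect on the estimates cannot be computed from the documents. This is more than a missing detail, because the rule makes the timing or existence of outcome data depend on adherence while the model treats each visit as one time point. It is worth correcting, but it does not undermine the pilot.

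**What to change.** In Table 1 and section 7.0:

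1. Keep the present anchor for dyads that complete session 6.
2. For randomised dyads that remain in the study but stop sessions early or never start, count both target dates from the date session 6 was due on the weekly schedule. That gives first and second targets of about week 8 and week 19, the same as for weekly-pace completers.
3. If on that date a dyad is still using the 12-week allowance (neither finished nor recorded as stopped), count from the date it stops sessions or the allowance ends, whichever is first. State where the 12 weeks start.
4. Record days from randomisation to each assessment and report them by arm.

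Item 4 does not remove the 6 to 7 week spread among completers, but it makes the spread, and any imbalance between arms, visible.

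The cost is protocol wording, a scheduling rule, and a recorded stop date and elapsed time per dyad. There are no extra assessments. The downside is that non-completers wait a few weeks longer for their calls, so a few more may be lost before the visit.
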